Participants must use highly effective birth control from 43 months after last dose of investigational medicinal product	Align with IB Ed 8.1	Synopsis, Section 5.2., Section 8.2.2., Section 8.2.3.
The following abbreviations were deleted: ECHO = echocardiogram ID = identification MAD = multiple ascending dose SAD = single ascending dose	These abbreviations are not used in the body of protocol amendment 4	List of Abbreviations
Updated information on completed and ongoing studies with mavacamten and number of participants enrolled	Align with IB Ed 8.1	Section 1.2.

Summary of Change	Reason for Change	Section(s)
Updated text describing clinical benefits and known risks of mavacamten	Align with IB Ed 8.1	Section 1.3.
Updated Study Schema to include telehealth visit at Week 222 and Early Termination	To align with Table 3	Study Schema
Deleted IMP Compliance for Week 222	Week 222 is now a telehealth visit	Table 3
Updated text on symptomatic overdose	Align with IB Ed 8.1	Section 7.6.
Added term dizziness as a likely risk of mavacamten use	Align with IB Ed 8.1	Section 8.1.
Updated so participants will report pregnancies any time from first dose to 43 months after last dose of mavacamten	Align with IB Ed 8.1	Section 8.2.3.
Participants must abstain from blood or plasma donation for 34 months after the final study visit	Align with data on long terminal elimination half-life of mavacamten in IB Ed 8.1	Section 9.4.

PROTOCOL SYNOPSIS

Title	An Open-label Extension Study of Mavacamten (MYK-461) in Adults with Symptomatic Obstructive Hypertrophic Cardiomyopathy Previously Enrolled in Study MYK-461-004 (PIONEER-HCM)
Study Number	MYK-461-008
Study Phase	2
Number of Centers	Up to 5 sites in the United States
Primary Objective	To assess the long-term safety and tolerability of mavacamten in individuals with symptomatic obstructive hypertrophic cardiomyopathy (oHCM)
Secondary Objectives	To assess in individuals with symptomatic oHCM the long-term effects of mavacamten on: 
 • Left ventricular outflow tract (LVOT) obstruction • Functional capacity • oHCM symptoms
Pharmacokinetic Objective	To perform population pharmacokinetics (PK) analyses in individuals with symptomatic oHCM receiving mavacamten
Study Design	
This is a Phase 2, open-label, multicenter study of adults with symptomatic oHCM who completed Study MYK-461-004 (PIONEER-HCM).
 
Participants in this study will be screened to ensure they continue to meet eligibility criteria. Participants are allowed to stay on background therapy with either beta blockers or calcium channel blockers.
 
Background cardiomyopathy therapy (eg, beta-blocker, verapamil, or diltiazem) may be adjusted or stopped after a participant has received 24 weeks of mavacamten treatment in this study as determined by the Investigator in conjunction with the MyoKardia Medical Monitor.
 
Once enrolled into Study MYK-461-008, participants will undergo baseline assessments and receive mavacamten once daily (QD) for a duration of up to approximately 5 years or until mavacamten becomes commercially available (at the discretion of MyoKardia).
 
Target dosing will be individualized for each participant based on his or her PK data obtained in the MYK-461-004 study. Specifically, the Target Dose for each participant will be individualized to obtain a steady-state trough plasma concentration of approximately 250 ng/mL to 500 ng/mL, based on PK modeling.
 
The starting dose will be 5 mg for all participants. Participants will return at Week 4 (± 4 days) for a plasma PK sample to measure drug levels and to undergo echocardiography to determine LVOT gradient (at rest, after a Valsalva maneuver, and after exercise) and left ventricular ejection fraction (LVEF). Participants will return at Week 6 (± 7 days) for evaluation of Week 4 results and dose adjustment to Target Dose.

	
Dose adjustment may also take place beyond Week 6 based on results of transthoracic echocardiogram (TTE), stress echocardiography and/or PK evaluation and based upon the opinion of the Investigator in conjunction with the MyoKardia Medical Monitor.
 
A stress echocardiogram will be administered at Week 48 and Week 72 to evaluate the post-exercise LVOT gradient and to determine whether further dose adjustment may be needed. If the post-exercise LVOT gradient is measured ≥ 50 mmHg, further dose adjustment may be considered and discussed with the MyoKardia Medical Monitor.
 
Dose adjustments beyond the Target Dose may only be exceeded for each given participant following discussion between the Investigator and the MyoKardia Medical Monitor. Lower doses are permissible.
 
The dose will not be increased if one or more of the following criteria are met:
 
• LVEF is $< 55\%$, and/or• LVOT gradient is < 30 mmHg after exercise, and/or• Trough mavacamten plasma concentration is > 350 ng/mL, and/or• A dose increase is not warranted in the clinical judgment of the Investigator 
Dose Reduction Rule: The dose may be reduced or discontinued in the case of an exaggerated pharmacologic effect at any time during the study based on the clinical judgment of the Investigator.
 
Participants who have had a dose adjustment (either in mavacamten or background cardiomyopathy therapy) should return to the clinic approximately 28 days later (± 7 days) for an unscheduled visit with resting TTE to confirm safety. Repeat of post-exercise echocardiographic assessment of LVOT gradient will be at the Investigator's discretion. Based on results and clinical symptoms at follow-up visits, subsequent dose adjustments will be discussed with the MyoKardia Medical Monitor.
 
Temporary Discontinuation: If results as reported by the central laboratories from any visit show mavacamten plasma concentration is ≥ 1000 ng/mL, or LVEF $< 50\%$ (as read by site), or Fridericia-corrected QT interval (QTcF) meets the following criteria, the participant will be notified by the study site/Investigator for further instructions.
 
• If QRS is narrow (< 120 milliseconds), then temporary discontinuation criteria are the smaller of: 15% increase from baseline QTcF OR QTcF ≥ 520 milliseconds• If QRS is wide (≥ 120 milliseconds), then temporary discontinuation criteria are the smaller of: a 15% increase from baseline QTcF OR QTcF ≥ 550 milliseconds 
If the participant is taking 5, 10, or 15 mg, study drug will be temporarily discontinued and he or she will return for an unscheduled visit (with electrocardiogram [ECG] and TTE assessments) 2 to 4 weeks later. If LVEF $\geq 55\%$ (as read by site) and QTcF < 500 milliseconds at the unscheduled visit, then the study drug will be restarted at a lower dose as shown below (previous dose \rightarrow restart dose):

--	---

	
• 5 mg → resume 5 mg• 10 mg → 5 mg• 15 mg → 10 mg 
Participants on 5 mg who have been temporarily discontinued on treatment based on clinical evaluation can be considered for dose reintroduction at 5 mg following agreement between the Investigator and the MyoKardia Medical Monitor.
 
If LVEF, plasma drug concentration, and/or QTcF persist out of range at the follow-up visit, then the participant will be discontinued from the study.
 
Participants who prematurely discontinue from the PIONEER-OLE study may be considered for rescreening for participation.
 
After Week 6, additional study visits will occur at Week 8 (\pm 7 days), Week 12 (\pm 7 days), and every 12 weeks (\pm 7 days) thereafter. Participants also will be contacted by phone in between clinic visits, at Week 18 and every 12 weeks thereafter. An end of study (EOS) visit will occur 8 weeks (\pm 7 days) after the last administration of study drug. Visits (including the Screening visit which serves as the baseline) will entail recording vital signs, targeted physical examination, ECGs, safety laboratory tests, N-terminal pro B-type natriuretic peptide (NT-proBNP), adverse events (AEs), New York Heart Association (NYHA) functional class, Kansas City Cardiomyopathy Questionnaire (KCCQ) score, and concomitant medications. Predose blood samples for assessment of drug concentration will be obtained at the time points indicated in the Schedule of Assessments. A standard TTE (including but not limited to assessment of LVOT gradient at rest and after Valsalva) will be performed at baseline and at the time points indicated in the Schedule of Assessments. In addition, a stress echocardiogram (with assessment of LVOT gradient post-exercise) will also be performed at baseline and at the time points indicated in the Schedule of Assessments.
 
For females of childbearing potential, pregnancy testing will be performed in clinic or at home every 4 weeks.
 
Participants will be followed through completion of EOS procedures. All AEs, including serious adverse events (SAEs), will be collected from the time of informed consent through the duration of the study, up to and including the Week 260/EOS visit. If there is a significant clinical abnormality or clinically significant laboratory abnormality in need of monitoring, the participant will be followed until resolution of the abnormality or until it is considered stable in the opinion of the Investigator.
 
End of Study (Week 260)
 
Participants who prematurely discontinue the study will attend an early termination visit and return to the study site 8 weeks later for an EOS visit.
 
Participants who complete 252 weeks of mavacamten treatment and do not rollover onto commercially available mavacamten will attend an end of treatment visit and return to the study site 8 weeks later for an EOS visit.

--	---

	
Participants who rollover onto commercially available mavacamten at any time will be contacted 8 weeks later by telephone or other technology for an EOS follow-up to assess AEs, concomitant medications, and pregnancy.
 
Telehealth Assessments
 
Telehealth assessments (conducted via telephone or other technology based on standard at institution) will be conducted at Weeks 18, 30, 42, 54, 66, 78, 90, 102, 114, 126, 138, 150, 162, 174, 186, 198, 210, 222, 234, and 246 to assess AEs, concomitant medications, and pregnancy.

Number of Participants	Up to 20 individuals with symptomatic oHCM will be enrolled.
Study Treatment	
Participants will receive mavacamten immediate-release capsules 5, 10, or 15 mg administered QD. The starting dose will be 5 mg for all participants.
 
Each participant has had a Target Dose determined based on his or her PK data from Study MYK-461-004. These doses may only be exceeded for each given participant following discussion between the Investigator and the MyoKardia Medical Monitor. Lower doses are permissible.
 
The Investigator, in conjunction with the Medical Monitor, may also elect to dose reduce a participant after they are on a stable dose of 10 mg or 15 mg treatment for 24 weeks or longer. Participants that have been dose reduced will undergo a follow-up visit 4 to 8 weeks (\pm 7 days) later (to mirror Week 8 assessments, including a TTE assessment). Based on results and clinical symptoms at follow-up visits, subsequent dose decisions will be discussed with the MyoKardia Medical Monitor. This cycle of potential dose reduction and follow-up can be repeated more than once (after at least 24 weeks on a stable dose of 10 mg or 15 mg treatment) and will need to be discussed with the MyoKardia Medical Monitor each time before it is carried out.

Study Duration	The study duration is 264 weeks (up to 4 weeks Screening, 252 weeks treatment [5 years], and 8 weeks posttreatment follow-up) unless the development of mavacamten is stopped or until mavacamten becomes commercially available (at the discretion of MyoKardia). If mavacamten clinical development is discontinued, this study will be terminated. The EOS is defined as the date of the last observation of the last participant.
Inclusion Criteria	
Each participant must meet the following criteria to be included in this study:
 
 1. Has completed Study MYK-461-004. Prior participation in a non-interventional observational study is allowed. 2. Able to understand and comply with the study procedures, understand the risks involved in the study, and provide written informed consent according to federal, local, and institutional guidelines before the first study-specific procedure 3. Body weight > 45 kg at Screening 4. Has safety laboratory parameters (chemistry and hematology) within normal limits (according to the central laboratory reference range) at Screening; however, a participant with safety

	
laboratory parameters outside normal limits may be included if he or she meets all of the following criteria:
 
 • The safety laboratory parameter outside normal limits is considered by the Investigator to be clinically unimportant • If there is an alanine aminotransferase or aspartate aminotransferase result, the value must be $< 3 \times$ the upper limit of the laboratory reference range • The body size-adjusted estimated glomerular filtration rate is ≥ 30 mL/min/1.73 m² 
5. Female participants must not be pregnant or lactating and, if sexually active, must use one of the following highly effective birth control methods from the Screening visit through 4 months after the last dose of investigational medicinal product.
 
 • combined (estrogen- and progestogen-containing) hormonal contraception associated with inhibition of ovulation or progestogen-only hormonal contraception associated with inhibition of ovulation by oral, implantable, or injectable route of administration • intrauterine device • intrauterine hormone-releasing system • bilateral tubal occlusion • Female participant is surgically sterile for 6 months or postmenopausal for 1 year. Permanent sterilization includes hysterectomy, bilateral oophorectomy, bilateral salpingectomy, and/or documented bilateral tubal occlusion at least 6 months prior to Screening. Females are considered postmenopausal if they have had amenorrhea for at least 1 year or more following cessation of all exogenous hormonal treatments and follicle-stimulating hormone levels are in the postmenopausal range. 
Male partners must also use a contraceptive (eg, barrier, condom, or vasectomy)


Exclusion Criteria
	
A participant who meets any of the following exclusion criteria may not participate in this study:
 
 1. Has QTcF > 500 milliseconds or any other ECG abnormality considered by the Investigator to pose a risk to participant safety (eg, second-degree atrioventricular block type II) 2. Since enrollment into Study MYK-461-004, has developed obstructive coronary artery disease ($> 70\%$ stenosis in one or more arteries) or known moderate or severe aortic valve stenosis 3. Since enrollment into Study MYK-461-004, has developed any acute or serious comorbid condition (eg, major infection or hematologic, renal, metabolic, gastrointestinal, or endocrine dysfunction) that, in the opinion of the Investigator or Medical Monitor, would pose a risk to participant safety or interfere with the study evaluation, procedures, or completion

	
 4. Has a positive serologic test at Screening for infection with human immunodeficiency virus, hepatitis C virus, or hepatitis B virus 5. Since enrollment into Study MYK-461-004, has developed clinically significant malignant disease 6. Is taking prohibited concomitant medications; background therapy on beta blockers or calcium channel blockers is allowed as long as the participant has been on a stable dose for at least 14 days prior to Screening 7. Has evidence of current abuse of drugs or alcohol or a history of abuse that, in the Investigator's opinion, would cause the participant to be noncompliant or would otherwise increase the risk to the participant 8. Is unable to comply with the study requirements, including the number of required visits to the clinical site.

Endpoints
	
Safety
 
 • Frequency and severity of treatment-emergent AEs and SAEs • Frequency of cardiovascular (CV) death • Frequency of sudden death • Frequency of CV hospitalization • Frequency of heart failure due to systolic dysfunction defined as a symptomatic LVEF < 50% • Frequency of myocardial infarction • Frequency of ventricular arrhythmias (ventricular tachycardia, ventricular fibrillation, ventricular flutter, torsade de pointe) • Frequency of syncope • Frequency of seizures • Frequency of stroke • Frequency of LVEF < 50% as measured by echocardiography • QT and QTcF intervals over time 
Efficacy and pharmacodynamics
 
 • Post-exercise, post-Valsalva, and resting LVOT gradient over time • NYHA functional class over time • KCCQ scores over time • NT-proBNP over time • Frequency of septal reduction therapy 
Pharmacokinetics
 
 • Mavacamten plasma concentration over time • Population PK

Sample Size and Statistical Considerations	No statistical hypothesis testing will be performed. Data will be summarized in tabular format, and concentration response plots may be constructed for selected variables. The sparse PK data will be combined with that of other studies to construct a population PK model across all studies.
In the context of COVID-19 or other pandemics, natural disasters, or major disruptions, provisions may be made to accommodate participants who are unable to attend onsite study visits for scheduled assessments and dispensation of mavacamten. Guidance on participant management in these situations is outlined in Appendix 4 .	

TABLE OF CONTENTS

PROTOCOL AMENDMENT SUMMARY OF CHANGES TABLE	2
PROTOCOL SYNOPSIS.....	4
TABLE OF CONTENTS.....	11
LIST OF TABLES	15
LIST OF FIGURES	15
LIST OF ABBREVIATIONS.....	16
1. INTRODUCTION	18
1.1. Background.....	18
1.2. Clinical Studies	18
1.3. Known and Potential Benefits and Risks.....	18
2. RATIONALE FOR THE STUDY AND FOR DOSE AND DOSING SCHEDULE	19
2.1. Rationale for the Study	19
2.2. Rationale for Dose and Dosing Schedule	19
3. STUDY OBJECTIVES	21
3.1. Primary Objective.....	21
3.2. Secondary Objectives	21
3.3. Pharmacokinetic Objective.....	21
4. OVERALL STUDY DESIGN AND PLAN.....	21
4.1. Study Duration.....	25
5. SELECTION AND WITHDRAWAL OF STUDY POPULATION	30
5.1. General Study Population and Clinical Sites.....	30
5.2. Inclusion Criteria	30
5.3. Exclusion Criteria	31

QTcF	Fridericia-corrected QT interval
SAE	serious adverse event
SD	standard deviation
SOC	system organ class
SUSAR	suspected unexpected serious adverse reactions
TBL	total bilirubin
TEAE	treatment-emergent adverse event
TTE	transthoracic echocardiography, transthoracic echocardiogram
ULN	upper limit of normal
US	United States
UV	unscheduled visit
Wk	week

1. INTRODUCTION

1.1. Background

Hypertrophic cardiomyopathy (HCM), an autosomal dominant genetic disease, is defined clinically as unexplained left ventricular (LV) hypertrophy in the absence of known causes such as pressure overload, systemic diseases, or infiltrative processes (Gersh et al, 2011). The phenotypic hallmark of HCM is myocardial hypercontractility accompanied by reduced LV compliance, reflected clinically as reduced ventricular chamber size, often supranormal ejection fraction, and diastolic dysfunction. Mutations in cardiac myosin and other sarcomere proteins in participants with HCM appear to increase net power generation by the sarcomere (Chuan et al, 2012; Sommese et al, 2013; Sung et al, 2012), consistent with the generally hypercontractile state and impaired compliance of the myocardium observed clinically in participants with HCM.

Mavacamten is a novel small molecule allosteric modulator of striated muscle myosin that selectively targets cardiac myosin and reversibly inhibits its binding to actin. Mavacamten's profile of myosin modulation is predicted to reduce dynamic left ventricular outflow tract (LVOT) obstruction in participants with obstructive HCM (oHCM) by reducing systolic hypercontractility and dynamic obstruction in the near term and reducing ventricular hypertrophy with chronic treatment. MyoKardia is developing mavacamten for the treatment of adults with symptomatic oHCM to relieve obstruction, improve symptoms, and increase exercise capacity.

In nonclinical studies, mavacamten was specific for striated muscle myosin and selective for the cardiac isoform (see the mavacamten Investigator's Brochure [IB]). Its targeted mechanism of action and high degree of specificity were reflected in its pharmacology in vitro and in vivo, as well as in the toxicology and safety pharmacology. In a feline model of HCM with LVOT obstruction, treatment with mavacamten reduced contractility and relieved obstruction in an exposure-dependent manner (Stern et al, 2016). The totality of the pharmacodynamic (PD) and tolerability data observed to date can be interpreted as direct or indirect consequences of reduced cardiac contractility.

Please refer to the mavacamten IB for more detailed information on mavacamten.

1.2. Clinical Studies

As of 30 October 2020, 15 clinical studies to investigate the safety and tolerability, efficacy, and pharmacokinetic (PK) profile of mavacamten have been completed. A total of 635 participants with HCM, healthy participants, or participants with hepatic impairment were enrolled across the completed studies, 464 of whom were exposed to at least 1 dose of mavacamten. Additionally, 294 participants have been enrolled across 3 ongoing studies of mavacamten. The results of the completed studies, as well as a description of the design and participants of the ongoing studies, are described in the IB.

1.3. Known and Potential Benefits and Risks

In nonclinical studies, safety testing in other mammalian species has demonstrated that dose-limiting toxicity is related to exaggerated pharmacologic effect and not to off-target adverse effects. Experiments with isolated adult rat ventricular myocytes in vitro and with anesthetized

rats in vivo have established that the pharmacological effects of mavacamten may be counteracted by positive inotropes (isoproterenol, dobutamine, or levosimendan).

Of the 18 clinical studies of mavacamten to date, clinical study reports are available for 15 studies. Overall, mavacamten appears well-tolerated with little evidence for off-target toxicity. In participants with oHCM, the clinical benefits of mavacamten treatment in the extension study (MAVA-LTE), which relies exclusively on clinical measures of cardiac function (including site-read echocardiographic measures) and participants' symptoms to guide dose titration, are consistent with the EXPLORER-HCM parent study, in which dose optimization was guided in part by plasma drug concentrations, specifically:

- reduced LVOT gradients
- improved New York Heart Association (NYHA) class
- improved diastolic function
- decreased left atrial volume index
- reduced wall stress (as measured by N-terminal pro B-type natriuretic peptide [NT-proBNP])

The known risks of mavacamten use from available nonclinical and/or clinical data to date include dizziness and cardiac failure due to systolic dysfunction (symptomatic left ventricular ejection fraction [LVEF] < 50%). Systolic heart failure is due to mavacamten's exaggerated on-target effect of reduction in cardiac contractility (ie, reduced LVEF). Potential risks of mavacamten use include embryofetal toxicity (observed in animal studies only), heart failure due to interaction with cytochrome (CYP) 2C19 and potent 3A4 inhibitors, and arrhythmia due to QT prolongation (observed in animal species and healthy volunteers).

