10.1.2. Adverse Events

- According to the International Council for Harmonisation (ICH) guideline for GCP, an AE is defined as any untoward medical occurrence in a clinical investigation participant administered a pharmaceutical product; it does not necessarily have to have a causal relationship with this treatment.
- An AE can therefore be any unfavorable and unintended sign (eg, tachycardia, enlarged liver, clinically important or abnormal laboratory finding), symptom (eg, nausea, chest pain), or evidence of disease activity temporally associated with the use of a study medication, whether or not related to the study medication.
- Each AE should be recorded as a single diagnosis. Accompanying signs (including abnormal laboratory values or ECG findings) or symptoms should not be recorded as additional AEs. If a diagnosis is unknown, signs or symptoms should be recorded appropriately as a PTAE or AE.
- Any new disease or exacerbation of an existing disease (eg, a worsening in the character, frequency, or severity of a known condition) is an AE except as described below:
 - Preexisting medical conditions (present at the time of signing of informed consent) are considered concurrent medical conditions and should not be recorded as PTAEs or AEs. However, if the participant experiences a worsening or complication of such a concurrent condition, the worsening or complication should be recorded appropriately as a PTAE (worsening or complication occurs before the first dose of study drug) or an AE (worsening or complication occurs after the first dose of study drug). Investigators should ensure that the event term recorded captures the change in the condition (eg, “worsening of ...”).
- Recurrence of an intermittent medical condition (eg, headache) not present prior to the first dose of study drug
- Any deterioration in a laboratory value or other clinical test (eg, ECG, X-ray) that is associated with symptoms or leads to a change in study treatment or concomitant treatment or discontinuation from study drug

The following additional points should be considered for PTAEs and AEs:

- Preplanned medical or surgeries or procedures
 - Preplanned surgeries or procedures that were scheduled prior to signing of informed consent are not considered PTAEs or AEs. However, if a planned procedure is performed early (eg, as an emergency) due to worsening of a preexisting condition, the worsening of the condition should be captured appropriately as a PTAE or AE.

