- Hospitalization for elective surgeries or procedures
 - Elective procedures performed for which there is no change in the participant's medical condition should not be recorded as PTAEs or AEs.
 - A hospitalization that was planned prior to the study or was scheduled during the study when the elective surgery or procedure became necessary because of the expected normal progression of the disease should not be recorded as PTAEs and AEs.
- Insufficient clinical response (lack of efficacy)
 - Insufficient clinical response, lack of efficacy, or pharmacologic action should not be recorded as an AE. The Investigator must make the distinction between exacerbation of preexisting medical condition and lack of therapeutic efficacy.
- Overdose
 - Cases of overdose with any medication without manifested side effects are not considered PTAEs or AEs.

The following should not be recorded as PTAEs or AEs:

- Any clinically significant abnormal laboratory findings or other abnormal safety assessments that are associated with the disease/disorder being studied, unless judged by the Investigator to be more severe than expected for the participant's condition
- The disease/disorder being studied or expected progression, signs, or symptoms of the disease/disorder being studied, unless more severe than expected for the participant's condition
- Situations in which an untoward medical occurrence did not occur (social and/or convenience admission to a hospital)
- Anticipated day-to-day fluctuations of a preexisting disease or condition present or detected at the start of the study that do not worsen

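### The lack-of-efficacy clause in Section 10.1.2 is ambiguous: read literally, it keeps pharmacologic action out of AE recording and conflicts with the rules that make a treatment-stopping LVEF fall an AE

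*Combined protocol and SAP*

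**What the plan says.** The clause stands in Section 10.1.2, in the bullet on insufficient clinical response: "Insufficient clinical response, lack of efficacy, or pharmacologic action should not be recorded as an AE". The sentence after it reads "The Investigator must make the distinction between exacerbation of preexisting medical condition and lack of therapeutic efficacy".

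Earlier in the same section, the AE definition lists a deterioration in a laboratory value or other clinical test that is symptomatic or "leads to a change in study treatment or concomitant treatment or discontinuation from study drug". Section 9.3 adds that abnormal findings the Investigator judges clinically important are recorded as AEs.

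On the nature of the harm, Section 1.3 says of nonclinical testing that "dose-limiting toxicity is related to exaggerated pharmacologic effect and not to off-target adverse effects", and of the clinical risk that "Systolic heart failure is due to mavacamten's exaggerated on-target effect of reduction in cardiac contractility". Section 5.5.1 and the title of Section 7.5 both gloss exaggerated pharmacologic effect as systolic dysfunction. Section 4 stops dosing when the site-read LVEF is below 50%.

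The first safety endpoint in the Synopsis and Section 11.2.1 is "Frequency and severity of treatment-emergent AEs and SAEs".

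**The concern.** In many protocols a dropped *lack of* would do no harm. Here the words that fall inside the exclusion are close to the protocol's own name for the drug's main known risk. A site reading the clause as punctuated does not have to stretch it to cover a fall in LVEF.

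The recording rule feeds the first-listed safety endpoint, which serves the primary objective of long-term safety and tolerability. If an on-target event is not entered as an AE, it has no severity grade and no causality assessment, and it cannot appear in the table of TEAEs leading to permanent discontinuation. Sites could also differ in which sentence they follow. Within the TEAE tables, following the literal exclusion can only lower the counts.

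**Working it through.** The protocol gives no figure to reproduce: Section 11.1 plans no hypothesis test and derives no sample size. The check is therefore mainly textual.

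**Step 1. One event under each rule.** Take a participant with a site-read LVEF of 31 to 49%.

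| Provision | Result for this event |
|---|---|
| Section 4, dose reduction rule | LVEF is below 50%, so dosing is stopped |
| Section 10.1.2, AE definition | A test deterioration that changes study treatment, so an AE |
| Section 9.3 | An AE if the Investigator judges it clinically important |
| Section 10.1.2, lack-of-efficacy bullet, read literally | Pharmacologic action, so not an AE |
| Section 10.1.2, same bullet, read as lack of action | Does not apply |
| Section 10.1.4, AESI | Does not apply, because the threshold is 30% or less |

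The literal reading contradicts the second and third rows. The other reading contradicts nothing. No sentence says which provision governs.

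**Step 2. What an omission would remove.** Section 10.2.1 captures relationship to study drug for TEAEs. Section 11.3.8.1 analyses AEs by incidence, severity and relationship, and tabulates TEAEs leading to permanent discontinuation. All of these start from an AE record.

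**Step 3. What would remain.**
- The count of LVEF below 50% by echocardiography (Section 11.2.1) does not depend on AE recording. It carries no severity or relatedness.
- Heart failure due to systolic dysfunction, meaning symptomatic LVEF below 50%, is a separate endpoint (Section 11.2.1). The protocol names no dedicated form for it; Section 10 names specialized eCRFs only for myectomy and septal ablation. Its symptom component may therefore rest on AE recording.
- LVEF of 30% or less is an AESI with 24-hour reporting (Section 10.1.4).
- Reasons for permanent discontinuation go on the eCRF (Section 5.5.1), and reasons for early discontinuation are tabulated (Section 11.3.3).

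**Step 4. Scale.** The denominator is the safety population (Section 11.3.8.1), with at most about 20 participants (Sections 5.1 and 11.1). If k affected participants are not recorded, the relevant row falls by 100 × k / n percentage points. At n = 20:
- k = 1: 100 × 1 / 20 = 5 points
- k = 2: 100 × 2 / 20 = 10 points
- k = 3: 100 × 3 / 20 = 15 points

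The documents give no value for k, which could be 0; the values above are assumptions that show the scale. The row for any TEAE falls only if the participant has no other recorded TEAE.

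**The case against.** The strongest reply is that the context settles the meaning. The bullet's heading concerns insufficient response, and the sentence after the clause deals only with lack of efficacy. When the protocol means harm it normally writes of an exaggerated effect, and the clause does not use that term. The closing list in Section 10.1.2 of things not to record has four items, and none is an on-target effect. Making LVEF of 30% or less an AESI only makes sense if reduced LVEF can be an AE. The causality factors in Section 10.2.2.3, which include dechallenge and amount of exposure, presuppose that drug-effect events are recorded. Systolic heart failure that leads to hospitalization would also meet the SAE definition.

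Most of this stands. It makes lack of pharmacologic action the probable intent, and it rules out two inferences that a reader might draw. The first is that the protocol instructs sites to leave out the drug's main harm; the surrounding text points the other way. The second is that the harm would vanish from the safety analysis; the separate endpoints, the AESI and the disposition reasons prevent that.

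The reply does not remove the contradiction in the printed rule. Section 9.3 depends on Investigator judgment, the AESI does not reach LVEF of 31 to 49%, an event in that band without hospitalization need not be an SAE, and the echocardiographic count does not feed the TEAE tables.

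**Conclusion.** The point holds as an ambiguity in an operative recording rule. Read literally, the clause conflicts with Section 9.3 and with the AE definition in its own section for an LVEF below 50% that stops dosing. The exposure is confined to LVEF of 31 to 49% and to the TEAE incidence, severity, relatedness and discontinuation summaries. It arises only if a site follows the literal wording.

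The size of any loss is unknown. Each omitted participant is worth 5 percentage points at n = 20, and more if fewer enrol. A reader might infer a definite understatement of the TEAE rate, but that needs an assumed number of events and an assumed number of sites misreading the clause; the documents give neither. Nor should the dose-limiting-toxicity sentence in Section 1.3 be taken as clinical evidence, because it describes other mammalian species. The clinical support is the later statement there on systolic heart failure.

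**What to change.** In Section 10.1.2:
- Change the clause so that it ends *lack of efficacy, or lack of pharmacologic action*.
- Add a sentence saying that exaggerated pharmacologic effects meeting the section's existing criteria (symptomatic, or leading to a change or stop of study treatment) are recorded as AEs.

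At data cleaning, check each hold or discontinuation for LVEF below 50% against an AE record and query any without one.

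This changes recording only and leaves treatment rules as they are. Section 13.4 allows an Administrative Letter for clarifications and for correcting inconsistencies, so a full amendment may not be needed. The cost is a few more reported TEAEs and one data-cleaning check.
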